Objectives	To assess the efficacy of antihistamines in the treatment of eosinophilic esophagitis. Primary outcomes are the number of eosinophils on histology and safety. Secondary outcomes are changes in dysphagia symptom questionnaire score, EoE endoscopic reference score, and the percentage of patients with histologic response of ≤15 eos/hpf on biopsy.			
Number of Subjects	The planned sample size is 20 patients in each arm, for a total of 40 study patients. Assuming a dropout rate of 20%, the goal is to enroll 50 patients.			
Diagnosis and Main Inclusion Criteria	Consentable, nonpregnant adults with a diagnosis of eosinophilic esophagitis			
Study Product, Dose, Route, Regimen	Famotidine 40 mg tab twice daily by mouth and loratadine 10 mg tab once daily by mouth for 12 week duration.			
Duration of Administration	12 weeks			
Reference therapy	Placebo			
Statistical Methodology	Patients will be randomized in a 1:1 fashion by a computer generated program. The changes in peak counts and questionnaire scores in the treatment arm from baseline to 12 weeks will be compared using a paired t-test or signed rank test. Categorical demographic variables and percentage of patients with histologic response of ≤15 eos/hpf at 12 weeks will be compared between the two arms using Chi-squared test or Fisher's exact test.			

1 Introduction

This document is a protocol for a human research study. This study will be carried out in accordance with the applicable United States government regulations and Mayo Clinic research policies and procedures.

1.1 Background

Eosinophilic esophagitis (EoE) is a clinicopathologic condition generally occurring in children and young adults characterized by symptoms of esophageal dysfunction and histologically by ≥ 15 eosinophils per high power field. It is hypothesized to be an immune and antigen-driven effect, which is limited to the esophagus. [1] First characterized less than 30 years ago, it is the most prevalent cause of esophageal symptoms among children and young adults. [2] The most prominent symptom in adults is the feeling of food sticking in the chest after swallowing, and EoE is the most common cause of food bolus obstruction.[1] Prominent symptoms of dysphagia are secondary to inflammation leading to progressive esophageal fibrosis, strictures, and narrowing.[3]

Guidelines on the diagnosis and management of EoE were first published in 2007, and updated in 2011. [4] These guidelines required clinical and/or histologic unresponsiveness to a PPI trial for the diagnosis of EoE, with the elimination of other causes of esophageal eosinophilia. [2] EoE and GERD were felt to be mutually exclusive. [4] A new condition was defined in guidelines published in 2011, 2013, and 2014 describing PPI-responsive esophageal eosinophilia (PPI-REE). [4] These patients had evidence of esophageal dysfunction and lacked the typical features of GERD, however responded to treatment with a high dose PPI trial. More recently, consensus guidelines have advocated for the removal of a PPI trial in the diagnosis of EoE. [5] Recent studies have shown that the clinical, histologic, and endoscopic features of EoE and PPI-REE are indistinguishable, and that GERD and EoE may share a complex relationship and can occur together. [4]

To date, the optimal therapy for EoE is undetermined, and limited by a lack of approved medications. [4] Treatment options include PPIs, corticosteroids, and diet modifications. Currently, PPIs are the first line treatment option. In a systematic review and meta-analysis, PPI therapy was found to have a clinical response in 60.8% of patients and histologic remission in 50.5%. [2] Proton pump inhibitors have two hypothesized mechanisms of action. First, they reduce the acidity of stomach fluids, and may reduce symptoms when reflux occurs. However, the role of reflux in the pathogenesis of EoE is unclear. Secondly, PPIs may also reduce inflammation in the esophageal epithelium by direct effects on the eotaxin-3-eosinophil pathway, reducing the eosinophil response. [6] The response to PPI therapy is higher in patients with documented GERD (70%) versus those with negative esophageal pH monitoring (29%).[2]

In patients who do not respond to a PPI, corticosteroids are the next preferred treatment. Topical corticosteroids have established efficacy in EoE, however their use remains off-label which limits insurance coverage. [7, 8] Additionally, there are no formulations specifically for esophageal delivery, and asthma preparations such as fluticasone inhalers or aqueous budesonide are used. For inhalers, the medication is swallowed rather than inhaled to coat the esophagus and

provide an anti-inflammatory effect. [9] The dosing and delivery method may be confusing for patients when compared to the instructions on the package insert. [5] Side effects of corticosteroids include oral and esophageal candidiasis. [5] Other long-term side effects include bone thinning, weight gain, and diabetes. Although studies have evaluated the ability of corticosteroids to induce remission, EoE is a chronic disease and further studies are needed to assess long term management. Symptoms of EoE generally relapse within several weeks of discontinuation of topic corticosteroid treatment. [10] Other medications under evaluation include prostaglandin receptor antagonists, immunomodulators such as azathioprine and 6-mercaptopurine, and biologic agents. [10]

Treatment also includes diet modification. The "six food elimination diet" is the most common dietary approach, with elimination of dairy, wheat, eggs, soy, nuts, seafood, and shellfish. [1] If symptoms improve, repeat endoscopy is performed after 12 weeks to document resolution of inflammation. This strategy is resource and cost intensive.[1] With the use of the six food elimination diet, triggers are identified, however long-term adherence to a specific diet is difficult. [5]

Allergists are well-established in the understanding and pathogenesis of EoE. They play a role in the management of atopic comorbidities, including asthma, allergic rhinitis, atopic dermatitis, and food allergies. Although the pathophysiology of EoE suggests an immune, antigen-mediated reaction, no study has evaluated the efficacy of antihistamines for treatment. Histamine is well characterized in the acute inflammatory and allergic response, and histamine receptors are present on eosinophils, T cells, monocytes, and dendritic cells. All are capable of producing and secreting histamine.[11] The histamine 1 and 2 receptors (H1R and H2R) are expressed not only on these immune cells, but ubiquitously throughout the gut wall. [12] In the gastrointestinal tract, histamine has three major functions; the enhancement of gastric acid production, modulation of gastrointestinal motility, and alteration of mucosal ion secretion. [12] There is a strong hereditary pattern of EoE with multiple implicated genes, which are more closely related to those involved in allergen sensitization and squamous epithelial cell dysfunction.[13] Based on the evidence that the allergic response plays an important role in the pathogenesis of EoE, anti-histamines may provide treatment benefit.

The purpose of this study is to evaluate the efficacy of anti-histamines in the treatment of EoE.

1.2 Investigational Agent

The investigational agents are famotidine 40 mg tablet twice daily by mouth and loratadine 10 mg tablet once daily by mouth for 12 week duration. Famotidine is an H2-receptor antagonist that inhibits the action of histamine at the histamine H2-receptors. Famotidine is FDA approved for the treatment of duodenal ulcer disease, erosive esophagitis, gastric hypersecretion, gastric ulcer, gastroesophageal reflux disease, and indigestion. Loratadine is a long-acting tricyclic antihistamine, which selectively blocks histamine H1 receptor activity. FDA approved uses include idiopathic urticaria and seasonal allergic rhinitis.

1.3 Clinical Data to Date

Although there is published data supporting the use of famotidine in peptic ulcer disease and gastroesophageal reflux disease, there currently is not study data for its use in EoE. Loratadine has published data for the treatment of urticaria and seasonal allergies, however has not been used in the treatment of EoE.

1.4 Dose Rationale

Loratadine 10 mg tablet daily is the standard dosage for the treatment of seasonal allergic rhinitis and idiopathic urticara. As EoE is an immune and allergen-mediated disease, we hypothesize the standard dosage will be effective in EoE. Similarly, famotidine 40 mg tablet twice daily is the standard dose for the treatment of peptic ulcers and gastroesophageal reflux disease. As stated in the background, gastroesophageal reflux may play a role in the pathogenesis of EoE. We hypothesize the standard dose of famotidine will be effective in EoE.

1.5 Risks and Benefits

Both famotidine and loratadine are over-the-counter medications, which are available to the general population without a prescription. Risks associated with these medications include their known common side effects, such as headache, dizziness, constipation, diarrhea, dry mouth, fatigue, somnolence, esophagitis, abdominal pain, constipation, and diarrhea. Other rare but serious side effects include rash (including but not limited to Stevens-Johnson syndrome and toxic epidermal necrolysis), arrhythmia, pancreatitis, bone marrow suppression (including but not limited to agranulocytosis, aplastic anemia, pancytopenia, thrombocytopenia), liver injury/failure, rhabdomyolysis, seizure, anaphylaxis, angioedema, and pneumonia. The risks are reasonable in relation to the anticipated benefits of a therapeutic response as these medications are generally well tolerated, over-the-counter, and used at the same dosing in other allergic and gastrointestinal disorders. The risks will be stated in the consent form.

2 Study Objectives

Primary Objective

To assess the efficacy of H1 and H2 antihistamines in the treatment of EoE through a decrease in the esophageal eosinophil count on biopsy. To assess the safety and tolerability of H1 and H2 antihistamines in subjects with EoE.

Secondary Objective

To determine whether loratedine and famotidine are effective for improving symptoms of EoE as measured by the Dysphagia Symptom Questionnaire (DSQ). To assess the percentage of patients with histologic response of \leq 15 eos/hpf on biopsy. To assess the percentage of patients with endoscopic response as measured by the EoE Endoscopic Reference Score (EREFS).

3 Study Design

3.1 General Description

[figure not shown]
This is a randomized, placebo-controlled phase II trial of the safety and efficacy of loratadine and famotidine in the treatment of EoE. Response to treatment will be assessed by questionnaires and endoscopy with histopathology. The expected duration of subject participation is 14 weeks. Subjects will be screened at outpatient clinic visit appointments and interested qualified subjects will be consented and offered participation in this trial. Once consent has been obtained, subjects complete the Dysphagia Symptom Questionnaire daily for two weeks. At week two, subjects will begin treatment and follow-up for the next 12 weeks. The study will be preceded by a washout period of at least 6 weeks followed by daily completion of DSQ for two weeks and active or placebo administration for 12 weeks. Participants will have monthly phone visits to monitor for adverse events and monitor compliance while on treatment. A final office visit for evaluation and repeat endoscopy will be conducted at the end of the study. During the final two weeks of treatment, subjects will again complete the DSQ daily. All data will be entered in a prospective automated institutional database (Redcap).

3.2 Number of Subjects

The planned sample size is 20 patients in each arm, for a total of 40 study patients. Assuming a dropout rate of 20%, the goal is to enroll 50 patients. The estimated baseline mean eosinophil count is expected to be between 80-110 eos/hpf, with an estimated standard deviation of change from baseline in eosinophil counts of 30-50 eos/hpf. Using a conservative standard deviation assumption of 50 eos/hpf, a sample size of 25 patients in each arm provides 80% power to detect a significant between group difference of 40%. Using a conservative standard deviation assumption of 50 eos/hpf, a sample size of 16 patients in each arm provides 80% power to detect a significant between group difference of 50%.

3.3 Duration of Participation

Each subject will participate for 12 weeks randomized to the study drugs or placebo.

3.4 Primary Study Endpoints

To determine whether loratedine and famotidine are effective for improving maximum eosinophil counts (eos/hpf) after 12 weeks of therapy with antihistamines in patients with EoE. To assess the safety and tolerability of H1 and H2 antihistamines in subjects with EoE.

3.5 Secondary Study Endpoints

To determine whether loratedine and famotidine are effective for improving symptoms of EoE as measured by the validated Dysphagia Symptom Questionnaire after 12 weeks of therapy with antihistamines.

To determine whether loratedine and famotidine are effective for improving the percentage of patients with histologic response of ≤ 15 eos/hpf after 12 weeks of therapy with antihistamines.

To determine whether loratadine and famotidine are effective for improving the endoscopic manifestations of EoE as measured by the validated EoE Endoscopic Reference Score.

3.6 Primary Safety Endpoints

All adverse events will be reported. A safety assessment will be performed monthly via phone visits after initiation of treatment, and at the 12-week follow-up visit with vital signs and a physical examination.

The EGD with biopsies to be performed at 12 week follow-up carries the standard risks associated with this procedure: complications from conscious sedation, performing endoscopy and biopsies. These risks include cardiac or respiratory compromise, allergic reactions to the medications used for sedation, perforation, bleeding and aspiration. The most significant risk is that of cardiovascular events estimated at .003%.[14] Though these risks are present, they are very low.

3.7 Identification of Source Data

The DSQ and EREFS scores will be entered into a computer database along with the patients' age, gender, and endoscopy and pathology reports from the electronic medical record. The data will be stored on the Mayo network hard-drive through the principal investigator's account.

4 Subject Selection Enrollment and Withdrawal

4.1 Inclusion Criteria

- 1. Patients over the age of 18, male and female.
- 2. Patients who carry the diagnosis of EoE based on esophageal biopsies obtained within 6 months prior to enrollment (>15 eosinophils per hpf on at least 2 esophageal levels)
- 3. Subjects must be able to give appropriate informed consent

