4.2 Exclusion Criteria

- 1. Not willing or able to sign consent.
- 2. Patients who have used topical or systemic corticosteroid therapy for any reason in the previous 6 weeks.
- 3. Patients who have been treated with acid-suppressing medications (PPI or H2 receptor antagonists) in the previous 6 weeks.
- 4. Patients on immunosuppressive or immunomodulating medications in the previous 6 weeks.
- 5. Patients with known allergies or hypersensitivity to anti-histamines.
- 6. Patients who have contraindications to the procurement of biopsies including patients who have known bleeding disorders, a history of bleeding diathesis, or who are currently using warfarin or clopidogrel.
- 7. Patients who have a contraindication to the performance of an esophagogastroduodenoscopy (EGD) including previous cardiopulmonary arrest during an endoscopic procedure.
- 8. Patients who are pregnant.

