4.3 Subject Recruitment, Enrollment and Screening

After institutional review board approval, all patients who present to the Mayo Clinic Florida Esophageal Diseases Clinic or General Gastroenterology Clinic with the diagnosis of EoE who meet enrollment criteria will be offered enrollment into the study. All enrolled patients will be entered by the physician through written informed consent.

The appointment schedule for the Esophageal Diseases clinic and the General Gastroenterology clinic at the Mayo Clinic Florida will be reviewed 1-5 days in advance by the study coordinator to determine which patients are coming for dysphagia or EoE. If the indication for the appointment is dysphagia, the study coordinator will review the patient's chart or outside records to determine if there is evidence of EoE. The physician that is scheduled to see any patient that is identified as having EoE will be contacted prior to the patients' appointment and asked if he or she agrees to have the patient approached for study enrollment.

We will also make general announcements to our Gastroenterology Division about the study in an attempt to recruit patients with EoE at our center.

Once patients are identified, they will be approached by our study coordinator and informed of the study. They will be provided with a consent form. The consent form will be documented by their signature on the consent form and this will be entered into the patient's permanent medical record.

Consent will either be performed in person face-to-face on the Mayo Clinic Florida Campus in a private meeting room, or via Zoom meeting, in the setting of the coronavirus pandemic. This will be per the patient preference. If consent is performed via Zoom meeting, the study coordinator or investigator will teleconference from a private exam or conference room on the Mayo Clinic Florida campus, and the study participant will teleconference from a private

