6.4 Visit 4 (12 week follow-up)

At the 12 week follow-up visit with a physician, we will review the results of the DSQ to be completed for weeks 10-12 of the study drugs. The 12 week follow-up appointment will occur no earlier than 12 weeks after initiation of the study drug and no later than 14 weeks after initiation. The patient will meet with one of the study investigators, and be consented for an EGD. An EGD with esophageal biopsies will be performed. Prior to EGD, a complete blood count and basic

metabolic panel will be ordered as routine per institutional policy. Either KD or DF will perform the EGD in the endoscopy suite, per our institution's standard protocol. Any macroscopic abnormalities seen in the esophagus will be documented and photographed. Any lesions in the upper digestive tract seen on EGD will be biopsied and treated as deemed appropriate by the performing endoscopist. Biopsy specimens will be labeled and placed in a container and labeled with the patient's ID number.

The eosinophil count will be determined by the study pathologist for the post-treatment exam using a previously validated protocol. [2, 3] Four esophageal biopsies will be sampled from both the distal esophagus (3cm above the GE junction) and proximal esophagus (at least 10 cm above the GE junction) to maximize sensitivity of detecting eosinophils.[1] On each biopsy fragment, 5 high-power fields will be examined and the overall peak eosinophil count determined from the field deemed to be most inflamed from all esophageal levels and all high power fields. [4]

Symptomatic improvement will be defined as at least 2 levels on the dysphagia questionnaire.

Study Activity	Week 0 (initial enrollment appointment)	Week 6	Week 10	Weeks 14-16 (follow-up appointment)
Study Agent(s) (weeks 2-14)		X	X	
Informed consent	X			
Physician office visit with medication review and physical exam	X			X
Phone or office visit with study coordinator		X	X	
Pill count		X	X	X
Drug diary		X	X	
Adverse event evaluation		X	X	Х

B-HCG (non-menopausal females)	X		
Dysphagia Symptom Questionnaire (complete weeks 0-2 and 12-14)	X		X
CBC and BMP			X
EGD w/ biopsy			X

7 Statistical Plan

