7.2 Statistical Methods

Descriptive Statistics

Means and standard deviations will be used to summarize quantitative and continuous variables. These will include age, dysphagia questionnaire scores, and eosinophils per hpf on histology. Frequencies and percentages will be used to summarize categorical variables including gender; the proportion of patients that have symptomatic and histologic improvement in symptoms on placebo; and the proportion of patients that have symptomatic and histologic improvement in symptoms on anti-histamines.

Handling of Missing Data

We will perform data queries for missing dysphagia questionnaires and pathology reports.

Primary Hypothesis: Antihistamines are effective for the treatment of EoE and will result in symptomatic improvement as assessed by patient questionnaires and endoscopic and histologic improvement as assessed by endoscopic score and by eosinophil counts on biopsy.

Continuous demographic variables, peak eosinophil counts and dysphagia and GERD questionnaire scores at baseline and 12 weeks will be compared between the treatment and placebo arms using a two-sample t test or Wilcoxon rank sum test where appropriate. Categorical demographic variable and percentage of patients with histologic response of ≤15 eos/hpf at 12 weeks will be compared between the two arms using Chi-squared test or Fisher's exact test. The changes in peak counts and questionnaire scores in the treatment arm from baseline to 12 weeks will be compared suing a paired t-test or signed rank test

All tests will be two-sided with alpha level set at 0.05 for statistical significance.

Interim Analysis

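### The baseline eosinophil count rests on a qualifying biopsy up to 6 months old with no stated reader or tie to washout, so the treatment-arm paired test cannot isolate the drug effect; the randomised 12-week comparisons are not biased by this

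*Combined protocol and SAP*

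**What the plan says.** **Source of the baseline count.** Section 4.1 bases entry on "esophageal biopsies obtained within 6 months prior to enrollment", with more than 15 eos/hpf on at least two levels. Section 6.1 (Visit 1) lists no endoscopy. The activity table in section 6.4 marks endoscopy with biopsy only at weeks 14-16, and the Visit 4 text says "An EGD with esophageal biopsies will be performed". No section defines the baseline eosinophil count.

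**Therapy at the time of the biopsy.** The section 4.2 exclusions look back 6 weeks, for example "Patients who have used topical or systemic corticosteroid therapy for any reason in the previous 6 weeks"; acid suppressants and immunomodulators have the same window. Section 3.1 describes a washout of at least 6 weeks. Neither section requires the biopsy to come after it. Section 4.4.1 expects that some patients will have come off earlier medication and may worsen.

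**Reader and method.** Section 6.4 states: "The eosinophil count will be determined by the study pathologist for the post-treatment exam using a previously validated protocol". The sampling and field-counting rules follow in the same paragraph. Nothing equivalent is stated for the qualifying biopsy. Section 3.7 takes "endoscopy and pathology reports from the electronic medical record" without separating time points, and section 4.3 lets the coordinator use the "chart or outside records to determine if there is evidence of EoE".

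**Analysis.** Section 7.2 compares peak counts between arms at baseline and at 12 weeks, and compares the ≤15 eos/hpf proportion between arms. It then adds a paired test of "The changes in peak counts and questionnaire scores in the treatment arm from baseline to 12 weeks". The Study Summary repeats the paired test and the responder comparison but omits the between-arm test of counts.

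**The concern.** A paired test in one arm attributes the whole difference between two biopsies to treatment. Here the two biopsies can differ in at least four other ways:

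- **Therapy.** The first may have been taken on a drug that was later stopped.
- **Time.** They may be many months apart.
- **Reading.** The first may have been counted by a different reader, from a different number of fragments and fields. The outcome is a peak, so it depends on how many fields are searched.
- **Selection.** The first count had to exceed a threshold and the second did not.

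Selection tends to lower the second count and can imitate benefit. Stopping earlier therapy tends to raise it and can hide benefit. A reading difference can act either way.

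The primary objective in section 2 is worded as a decrease in the count. A reader of the Study Summary alone would take the paired test to be the primary efficacy test.

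**Working it through.** **1. The plan's own sample size.** Sections 3.2 and 7.1 give an SD of change of 50 eos/hpf, 80% power, and 25 or 16 per arm for a 40% or 50% difference; section 7.2 gives two-sided alpha 0.05. With n per arm = 2 × (1.960 + 0.842)² × SD² / difference²:

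- 40 eos/hpf: 2 × 7.849 × 2500 / 1600 = 24.5, so 25.
- 50 eos/hpf: 2 × 7.849 × 2500 / 2500 = 15.7, so 16.

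Both figures reproduce at a baseline mean of 100, which lies inside the stated 80-110 but is not itself stated. The power statement therefore concerns a difference between groups, although its SD is that of change from baseline.

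**2. Timeline.** Six months is about 26 weeks. The symptom diary takes 2 weeks before the first dose. The final visit falls "no earlier than 12 weeks after initiation of the study drug and no later than 14 weeks after initiation".

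- Longest gap between biopsies: 26 + 2 + 14 = 42 weeks, of which at most 14 follow the first dose. The dispensed supply is 12 weeks (section 5.6).
- Look-back not covered by the drug exclusions: 26 − 6 = 20 weeks.

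**3. Paired test with no drug effect.** Take n = 20 (planned evaluable patients per arm), the SD of change from section 7.1, and an assumed non-drug shift s; the documents give no value for s. The noncentrality is (s/SD) × √20 and the critical t on 19 degrees of freedom is 2.093.

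| Assumed shift | SD 50: noncentrality | SD 50: rejection | SD 30: noncentrality | SD 30: rejection |
|---|---|---|---|---|
| 0 | 0 | 5% | 0 | 5% |
| 10 | 0.894 | 13.6% | 1.491 | 29% |
| 20 | 1.789 | 39.7% | 2.981 | 81% |

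These rates depend only on s, SD and n. A placebo response of the same size, measured from a fresh and study-read baseline, would give the same values.

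**4. Plausible size of regression to the mean.** Assume normal counts, a single cut at 15 and test-retest correlation r. The expected fall is (1 − r) × SD × φ(a)/(1 − Φ(a)), with a = (15 − mean)/SD, where φ and Φ are the standard normal density and distribution function. SD here is that of the count, which the documents do not give; 30 and 50 are assumed. The two-level entry rule is not modelled.

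- Mean 80, SD 50: a = −1.30 and the selection excess is 9.5, so the fall is 4.7 at r = 0.5 and 7.1 at r = 0.25.
- Mean 110, SD 50: the excess is 3.4, so the fall is 1.7 and 2.5.
- SD 30: the fall is below 1 in every case.

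This treats 80-110 as the mean before selection. If it is instead the mean of enrolled patients, the pre-selection mean for the 80, SD 50 case is about 66 and the excess is 14.0, so the fall is 7.0 or 10.5. Regression from the threshold alone is therefore usually a few eos/hpf and reaches 10 only in the least favourable corner.

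**5. Randomised comparison.** If washout, time, reader and selection move both arms by s on average, the expected changes are s + drug effect and s, and their difference is the drug effect. The 12-week count and responder tests do not use the baseline at all. In simulation with 20 per arm and SD 50, common shifts of 0, 20 and 40 gave between-arm rejection of 5.1%, 5.0% and 5.0%.

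**The case against.** The strongest reply is that the trial is randomised, so its main evidence does not depend on the baseline biopsy. That stands. A reader might infer that the old biopsy biases the primary comparison or the responder analysis. The documents do not support this, because section 7.2 makes both comparisons between arms at 12 weeks.

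A reader might also take 14% and 40% as false-positive rates caused by a 6-month-old biopsy. They are not. The shifts are assumed, the rates apply to any uncontrolled paired test, and step 4 suggests that threshold selection alone would usually produce less than 10 eos/hpf.

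It is tempting to say that the bias flatters the drug. The mechanisms oppose each other and the net could be near zero. A patient biopsied on therapy must still have exceeded 15 eos/hpf on two levels; that limits the on-treatment scenario without removing it.

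Finally, one might state that baseline counts are taken from local pathology reports. Section 3.7 does not separate time points, and the study pathologist may have read some qualifying slides. What the text supports is that the baseline reader and method are not specified.

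The plan also nowhere ranks the paired test as the main evidence. That is fair for section 7.2, but the Study Summary names no other test for counts, so the ambiguity is in the plan itself.

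**Conclusion.** The concern holds for one analysis. The paired test of change in the treatment arm cannot be read as drug effect, because its baseline may be up to about 42 weeks older than the final biopsy, is not required to follow washout, and has no stated reader or counting method. The size and sign of the resulting bias cannot be derived from the documents; the rejection rates above illustrate sensitivity and do not estimate it. The conclusion assumes that the qualifying biopsy serves as the baseline. The documents do not say so, but they schedule no other pre-treatment endoscopy. The randomised 12-week comparisons of count and response keep their validity on this point.

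**What to change.** 1. In the Study Summary and section 7.2, name the between-arm comparison of the 12-week peak count as the primary efficacy test. Adjust it for the qualifying-biopsy count by ANCOVA, on a transformed or rank scale if counts are skewed.
2. Label the within-arm paired test descriptive, and state that the baseline count is the qualifying-biopsy count.
3. Add two case report form fields: the date of the qualifying biopsy and the EoE therapy at that date. Without them nobody can later tell which baselines were taken on therapy.

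The cost is SAP and synopsis wording plus the two fields; no extra procedure is needed. The downside is that an old baseline may correlate weakly with the 12-week count. ANCOVA multiplies the residual variance by 1 − r², which is 0.75 at an assumed r of 0.5 but 0.94 at 0.25, so the gain in precision may be small.

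Two additions are optional. The study pathologist could re-read retrievable qualifying slides, masked to arm and time point, but this cannot equalise how the oesophagus was sampled. A sensitivity analysis limited to off-therapy baselines would subset about 40 patients and would be imprecise.
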